7.5.1 PRECAUTIONARY MEDICATIONS, TREATMENTS, AND PROCEDURES

Not applicable.

7.6 PROHIBITED MEDICATIONS, TREATMENTS, AND PROCEDURES

Until a possible primary outcome is reached open label treatment of HZO eye disease with oral valacyclovir, acyclovir, or famciclovir is prohibited for duration of the study (i.e. 18 months).

7.7 PROPHYLACTIC MEDICATIONS, TREATMENTS, AND PROCEDURES

Not applicable.

7.8 RESCUE MEDICATIONS, TREATMENTS, AND PROCEDURES

Not applicable.

7.9 PARTICIPANT ACCESS TO STUDY AGENT AT STUDY CLOSURE

Following completion of the 18-month study the study participant will return to the care of their ophthalmologist and treated at their physician's discretion.

8 ASSESSMENT OF SAFETY

8.1 SPECIFICATION OF SAFETY PARAMETERS

It is the responsibility of the PCC Principal Investigator (PI) to oversee the safety of the study at his/her center. This safety monitoring will include training, careful assessment and appropriate reporting of serious adverse events (see MOP).

The CC monitoring of serious adverse events will be reviewed by masked medical monitors. These medical monitors will also have the ability to unmask treatment if required in an emergency for study participant safety (see MOP).

At each contact with the study participant, the PCC study investigator or designated study team member will assess for possible medical events of interest, possible primary endpoints and for possible SAEs (see MOP).

8.1.1 COLLECTION OF SELECTED ADVERSE EVENTS (AE)

Adverse events that result in temporary or permanent discontinuation of study medication will be required to be reported by the PCC to the CC as appropriate.

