According to the package insert regarding laboratory results, hematologic abnormalities occurred in 0-0.7% in adults treated with valacyclovir 1 gram daily compared to 0.8-1.5% of adults treated with placebo. In addition, AST (SGOT) liver function test abnormalities occurred in 4.1% of adults on valacyclovir 1000 mg daily, compared to 3.0% on placebo. With regard to geriatric use, elderly patients age 65 and over are more likely to have renal or CNS adverse events and hematological and liver function problems are not mentioned. With regard to adults with liver impairment including cirrhosis, dosage modification is not recommended. Despite widespread use, there is little evidence that oral acyclovir (valacyclovir is prodrug of acyclovir) causes significant liver injury, or changes in serum liver enzyme levels (http://ivertox.nih.gov/acyclovir.htm). Suppressive valacyclovir for HSV genital disease in immunocompetent patients at the same dose of 1000 mg daily and duration of one year, or longer, as used in our study has a long established safety profile with adverse events similar to placebo in numerous studies, both before and after its approval in 1995 (50). Longterm suppressive valacyclovir was not associated with laboratory abnormalities, including creatinine levels. Headache, nausea, and diarrhea were the most common adverse events attributed to the drug. Thrombotic microangiopathy that has been reported at high doses (8000 mg/d) for prolonged periods for prophylaxis of cytomegalovirus (CMV) infection, especially in severely immunosuppressed patients, has not been reported in 3050 participants in 4 trials of valacyclovir suppression of recurrent genital HSV.

If participants in this study develop side effects, such as gastrointestinal symptoms or headache, they will be instructed to take one tablet twice daily, as the study medication may be better tolerated in divided doses. Study participants with side effects that require discontinuation of the study medicine will continue to be followed, and be included in the study on an intention-to-treat basis. The study ophthalmologist will be allowed to restart the study medication after mild or moderate side effects resolve, if the study participant agrees. If side effects recur, the dose can be reduced to one pill daily, as this lower dose has been reported in a retrospective study to be effective in reducing recurrences in HZO (1).

Valacyclovir and Renal Insufficiency

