6.1.8 DOSE ADJUSTMENTS/MODIFICATIONS/DELAYS

Study investigators will be trained and study participants will be instructed regarding dose adjustments of study medication.

Use of Divided Dose of Study Medication for Intolerance

If the study participant has mild to moderate side effects to the study medication, the medication may be temporarily discontinued. The study participant may take one pill twice daily, instead of two pills once daily, as it may be better tolerated.

Use of Reduced Dose of Study Medication for Intolerance

If the study participant has mild to moderate side effects to the study medicine when taken in divided doses, the medication may be temporarily discontinued. The study participant may take a reduced dose of one capsule daily.

Discontinuation of Study Medication due to Intolerance

If intolerance to the study medication is moderate or worse after restarting the study medication in divided doses and reducing the dose, the study medication will be permanently discontinued. The study participant will be treated at the discretion of ophthalmologists involved in their care, and continue to be followed. Open label use of other antivirals after study medication is discontinued will be collected and monitored.

Discontinuation of Study Medication

If the study participant develops a contraindication to valacyclovir during the course of the study (See 5.2.). The study medication will be permanently discontinued and the study participant will continue to be followed.

Discontinuation due to Pregnancy

If a study participant becomes pregnant, the study medication will be discontinued and the study participant will continue to be followed. If a study participant thinks she may be pregnant, a pregnancy test will be performed.

Discontinuation due to Worsening Chronic Kidney Disease

If a study participant develops worsening chronic kidney disease with confirmed eGFR less than 45, the study medication will be discontinued and the study participant will continue to be followed.

Discontinuation due to Acute Kidney Failure

If a study participant develops acute kidney failure, and requires temporary or permanent dialysis, the study medication will be discontinued and the study participant will continue to be followed.

Temporary Discontinuation due to Vaccination Against Zoster

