7.3.3 FOLLOW-UP STUDY VISITS

Study visit number at 3, 4, 5 occurring at months 3, 6, and 9 after enrollment:

At the follow-up visits, the following activities will occur/be performed:

- Study specific history of HZO treatment.
- Study specific anterior segment ophthalmic exam.
- Assessment of post herpetic neuralgia score and review of medications taken for PHN.
- Returned study medication pills will be counted to assess medication compliance. Diaries will be returned.
- Assessment for possible medical events of interest
- Assessment for possible primary endpoints.
- Assessment for possible SAEs.
- Study participants will be dispensed an adequate supply of study medication and will receive instructions to take 2 pills once daily. in addition to any other medication(s). At the discretion of the investigator, dosage may be adjusted to one pill twice daily or once daily and appropriate study participant instruction sheet will be provided (see MOP).
- Study participants will receive a diary to record when study medication is taken.
- If the study participant had a baseline eGFR of 45-59 repeat eGFRs will be completed prior to the 3, 6, 9 month study visits.
 - o If eGFR is 45 or above, study medication will be continued.
 - If eGFR is less than 45, the study medication will be discontinued, and the eGFR will be repeated within one week. If on repeat testing the eGFR:
 - is 45 or more, the study medication will be resumed, and eGFR will be repeated within 30 days of the next study visit.
 - is less than 45, study participant will be given a prescription to visit their local study designated laboratory for monthly eGFR testing until it is 45 or more. In addition, study participants will be told to see their primary care doctor for management of their kidney disease. The study medication will not be resumed, and the study participant will continue to be followed in the study.
- An appointment to return during a specified window of days for their three-month follow-up visit will be scheduled.
- The study participant will be instructed to continue their non-study treatment.

The importance of compliance with the study medication and visits, will be emphasized at each study visit. Study participant's contact information will also be confirmed at each study visit (see MOP).

Visit 6 (12 month follow-up visit):

At this visit, study medication will be discontinued. The visit will be the same as the 3, 6, and 9- month follow-up visits, with the addition of:

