8.2 CLASSIFICATION OF AN ADVERSE EVENT

8.2.1 SEVERITY OF EVENT

Events that result in temporary or permanent discontinuation of study medication will be recorded on appropriate study eCRF (See MOP).

The intensity (or severity) of events will be rated on a three-point scale:

- Mild: Events that require minimal or no treatment and do not interfere with the participant's daily activities.
- Moderate: Events that result in a low level or inconvenience or concern with the therapeutic
 measures. Moderate events may cause some interference with functioning. Mild or moderates side
 effects to study medication may result in temporary or permanent discontinuation without being a
 serious adverse event.
- **Severe:** Events that interrupt a participant's usual daily activity and may require systemic drug therapy or other treatment. Severe events are usually potentially life-threatening or incapacitating.

It is emphasized that the term severe is a measure of intensity: thus, a severe adverse event is not necessarily serious. For example, itching for several days may be rated as severe, but may not be clinically serious.

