10.4.2 ANALYSIS OF THE PRIMARY EFFICACY ENDPOINT(S)

The primary endpoint is the time from randomization to development of the first occurrence of any new or worsening dendriform epithelial keratitis, stromal keratitis, endothelial keratitis, and/or iritis due to HZO, diagnosed by a change in clinical slit lamp biomicroscopy examination and accompanied by prespecified changes in treatment (see MOP) by 12 months of treatment with valacyclovir compared to placebo.

The objective of the analysis of the primary endpoint is to compare cumulative failure rates (failure defined as an episode of new or worsening dendriform epithelial keratitis, stromal keratitis, endothelial keratitis, and/or

iritis) in the valacyclovir treated groups with the placebo treated group by 12 months (treatment completion). Kaplan-Meier curves will be plotted by treatment group (overall and within strata) and 95% confidence intervals (adjusted for interim analyses) for the difference between the 12-month cumulative failure rates will be estimated (overall and within strata). Results will also be plotted within strata and by baseline disease and study participant characteristics to provide descriptive summaries of the results.

The primary study analysis will be based on a stratified log-rank (2-sided) test with adjustment for stratification factors (age, and recent onset vs. chronic disease).

Details of all analyses, including sensitivity analyses are provided in the SAP. For example, analyses will be provided that incorporate adjustments of study medication to one 500 mg pill twice daily or one 500 mg pill daily instead of the standard 2 pills daily; and that evaluate the impact of study drug discontinuation by treatment group.

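### Non-serious intolerance handled by dividing or reducing the dose without a pause has no stated adverse event reporting requirement, so an unknown share may be missing from the safety comparison

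*Combined protocol and SAP*

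**What the plan says.** **Reporting rule.** Section 8.1.1 states: "Adverse events that result in temporary or permanent discontinuation of study medication will be required to be reported". Section 8.2.1 repeats the condition for data capture: "Events that result in temporary or permanent discontinuation of study medication will be recorded on appropriate study eCRF". Sections 8.2.2 and 8.2.3 ask for causality and expectedness only for serious events and for adverse events that lead to discontinuation. None of the four names a divided or reduced dose.

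**Handling of intolerance.** Three sections describe it, and not in the same way.

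- Section 2.3.1, on participants with gastrointestinal symptoms or headache: "they will be instructed to take one tablet twice daily, as the study medication may be better tolerated in divided doses". No pause is mentioned at this step. One pill daily appears there only after a stop, a restart and a recurrence.
- Section 6.1.8: "If the study participant has mild to moderate side effects to the study medication, the medication may be temporarily discontinued", followed by "The study participant may take one pill twice daily, instead of two pills once daily, as it may be better tolerated". If side effects occur on divided doses, a pause is again optional, and "The study participant may take a reduced dose of one capsule daily".
- Section 7.3.3 gives the investigator discretion at follow-up visits: "dosage may be adjusted to one pill twice daily or once daily". No pause and no prior step are required.

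**Use of the data.** Section 10.4.2 plans analyses of the primary efficacy endpoint that take account of "adjustments of study medication to one 500 mg pill twice daily or one 500 mg pill daily", so dose changes must be captured somewhere. For safety events, 10.4.5 names rates of study drug termination, by arm and stratum, as the comparison.

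**The concern.** The reporting threshold does not match the protocol's own pathway for intolerance. A participant who moves to one pill daily at month 3 because of nausea, under 7.3.3 and without missing a day, creates no adverse event record that 8.1.1 requires. The dose change can enter an efficacy sensitivity analysis, but no section links it to the symptom that caused it.

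Section 2.3.1 says the study evaluates both efficacy and safety, in patients who are generally older than HSV patients. The background section asks whether the balance of risk and benefit varies by age at onset. For a preventive drug taken for a year, intolerance that changes how the drug is taken bears on that question. Section 2.3.1 also notes that discontinuation rates from prior studies are not listed, so outside figures quoted in the protocol cannot fill the gap.

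**Working it through.** **Step 1. Which routes meet the trigger?**

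| Route | Pause required? | Report required by 8.1.1? |
|---|---|---|
| 2.3.1, divided dose | not mentioned | no, unless a pause occurs |
| 2.3.1, one pill daily after stop, restart and recurrence | already stopped once | yes |
| 6.1.8, divided dose | optional | only if a pause is used |
| 6.1.8, one capsule daily | optional | only if a pause is used |
| 7.3.3, either change at a visit | not mentioned | no, unless a pause occurs |

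The gap is non-serious intolerance handled by a dose change with no interruption.

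**Step 2. What else could catch these events?** Section 8.3 requires all serious events to be recorded, whether or not drug is stopped. Medical events of interest are assessed at each follow-up visit (7.3.3, Table 1, 8.1), and 7.1.1 lists a medical event form. Their content is left to the MOP, which was not available. Nothing in the protocol says that they include tolerability symptoms or reasons for a dose change.

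**Step 3. How large could the loss be?** The plan states no figure to reproduce, and no section gives the share of intolerance handled without a pause. The following is therefore an illustration.

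- Arm size: about 390 (10.5).
- Incidence, valacyclovir vs placebo (2.3.1, package insert): abdominal pain 11% vs 6%, nausea 11% vs 8%, headache 35% vs 34%, dizziness 4% vs 1%.
- Assumption: a capture share c, the same in both arms.

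Expected count = 390 × incidence × c. For abdominal pain at c = 1 this is 390 × 0.11 = 42.9 and 390 × 0.06 = 23.4. At c = 0.5 it is 21.45 and 11.7. Counts are rounded for a two-sided Fisher exact test. Power is for a two-sided 5% normal-approximation test of two proportions, on unrounded rates.

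| Symptom | c | Counts | Difference (points) | Fisher p | Power |
|---|---|---|---|---|---|
| Abdominal pain | 1.00 | 43 vs 23 | 5.00 | 0.014 | 0.71 |
| | 0.75 | 32 vs 18 | 3.75 | 0.056 | 0.57 |
| | 0.50 | 21 vs 12 | 2.50 | 0.15 | 0.41 |
| | 0.25 | 11 vs 6 | 1.25 | 0.33 | 0.23 |
| Dizziness | 1.00 | 16 vs 4 | 3.00 | 0.011 | 0.77 |
| | 0.50 | 8 vs 2 | 1.50 | 0.11 | 0.47 |
| Nausea | 1.00 | 43 vs 31 | 3.00 | 0.18 | 0.30 |
| Headache | 1.00 | 137 vs 133 | 1.00 | 0.82 | 0.05 |

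The difference is c × (p1 − p2), so it shrinks in proportion to c. The relative risk is (c × p1)/(c × p2) = p1/p2, so it does not move: 0.11/0.06 = 1.83 for abdominal pain at every c.

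**Step 4. How far do these inputs reach?** They are incidences of any such symptom, not of symptoms that change dosing. Even the widened trigger would record fewer events than the c = 1 rows, so the table is a best case for what could be seen.

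**The case against.** **Selective collection is a declared choice.** The title of 8.1.1 says that only selected events are collected. The drug is approved at this dose for HSV suppression and has a long safety record (2.3.1). The primary safety endpoints are serious, unexpected, related events (8.1.2), acute kidney failure is the predominant concern (8.5), and tolerability is not a listed endpoint. This stands as a reason not to collect every adverse event. It does not explain why the threshold should miss events that alter dosing.

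**A reader might infer that most drug intolerance escapes the safety data.** The documents do not support that. No share is given, any temporary pause is reportable, and 6.1.8 offers a pause at both dose-change steps. Its later reference to restarting in divided doses suggests that a pause was expected. A participant who pauses and then does well on a divided dose is reported.

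**A reader might infer that halving the dose is a first response.** In 2.3.1 and 6.1.8 it is a later step; only 7.3.3 allows it directly.

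**A reader might infer bias toward no difference, because dose changes rescue more cases on valacyclovir.** That is plausible, but no section documents it, and the calculation above assumes equal capture. It shows lost events and power, not a distorted relative risk.

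**The examples matter.** Section 2.3.1 names gastrointestinal symptoms and headache. Nausea and headache would not separate the arms at the quoted rates even with complete reporting.

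**The MOP may already close the gap.** The medical event form or the dose-change record may ask for the reason. This cannot be excluded, and the sponsor can check it quickly.

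**Conclusion.** The point holds in limited form. As written, 8.1.1 and 8.2.1 to 8.2.3 place no adverse event requirement on non-serious intolerance that leads to a divided or reduced dose without a pause, and the termination summary in 10.4.5 does not pick it up. The share affected is unknown.

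If capture is incomplete but equal between arms, the absolute difference and the power fall and the relative risk does not. At an assumed 50% capture, the abdominal pain difference drops from 5.0 to 2.5 percentage points and power from 0.71 to 0.41. These figures rest on all-symptom package-insert incidences, 390 per arm and an assumed capture share. The textual gap does not depend on them. The conclusion would change if the MOP already requires the symptom behind each dose change to be recorded. The primary efficacy analysis is not in question.

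**What to change.** 1. In 8.1.1 and 8.2.1, extend the trigger to adverse events that result in a divided dose or a reduced dose, as well as temporary or permanent discontinuation. Carry the same wording into 8.2.2 and 8.2.3.
2. In 10.4.5, compare by arm the proportion with any adverse-event-driven dosing change, alongside study drug termination.
3. If the MOP already captures these events, say so in 8.1.1 and point to the form.
4. Reconcile 2.3.1, 6.1.8 and 7.3.3, which describe the sequence of pause and dose change differently. No view is taken here on which sequence is right.

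Items 1 to 3 change what is collected and summarised, not any dose or clinical rule. The cost is a wording change, a recorded reason for dose changes that 10.4.2 already needs, and a modest number of extra adverse event forms, mostly for mild or moderate events.

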8.1.2 DEFINITION OF SERIOUS ADVERSE EVENTS (SAE)

Serious, unexpected adverse events related to the study treatment will be primary safety endpoints. A serious adverse event is any untoward occurrence that:

- Results in death.
- Is life threatening; (a nonlife-threatening event which, had it been more severe, might have become life-threatening, is not necessarily considered a serious adverse event).
- Requires inpatient hospitalization or prolongation of existing hospitalization.
- Results in persistent or significant disability/incapacity or substantial disruption of the ability to conduct normal life functions.
- Is a congenital anomaly or birth defect.
- Is considered a significant medical event by the study investigator based on medical judgment (e.g., may jeopardize the study participant or may require medical/surgical intervention to prevent one of the outcomes listed above).
- The occurrence of the SAE acute kidney failure, defined as requiring temporary or permanent dialysis, will be a safety endpoint.

8.1.3 DEFINITION OF UNANTICIPATED (UNEXPECTED) PROBLEMS

OHRP considers unanticipated problems involving risks to participants or others to include, in general, any incident, experience, or outcome that meets all of the following criteria:

- Unexpected in terms of nature, severity, or frequency given (a) the research procedures that are described in the protocol-related documents, such as the IRB-approved research protocol and informed consent document; and (b) the characteristics of the participant population being studied;
- Related or possibly related to participation in the research ("possibly related" means there is a
 reasonable possibility that the incident, experience, or outcome may have been caused by the
 procedures involved in the research).
- Suggests that the research places participants or others at a greater risk of harm (including physical, psychological, economic, or social harm) than was previously known or recognized.

This study will use the OHRP definition of unexpected/unanticipated problems.

The determination that a serious adverse event is related to the study treatment is initially made by the study investigator, reviewed by the medical monitor and DSMC.

8.2 CLASSIFICATION OF AN ADVERSE EVENT

8.2.1 SEVERITY OF EVENT

Events that result in temporary or permanent discontinuation of study medication will be recorded on appropriate study eCRF (See MOP).

The intensity (or severity) of events will be rated on a three-point scale:

- Mild: Events that require minimal or no treatment and do not interfere with the participant's daily activities.
- Moderate: Events that result in a low level or inconvenience or concern with the therapeutic
 measures. Moderate events may cause some interference with functioning. Mild or moderates side
 effects to study medication may result in temporary or permanent discontinuation without being a
 serious adverse event.
- **Severe:** Events that interrupt a participant's usual daily activity and may require systemic drug therapy or other treatment. Severe events are usually potentially life-threatening or incapacitating.

It is emphasized that the term severe is a measure of intensity: thus, a severe adverse event is not necessarily serious. For example, itching for several days may be rated as severe, but may not be clinically serious.

